3.3 Exploratory Objectives

1. To find out if doxycycline treatment changes Lactobacillus-deplete microbiota to a Lactobacillus-dominated microbiota?

2. To find out if doxycycline treatment, improves the differentiation potential and colonyforming activity of endometrial stromal cells?

3. To find out if CE is related to heightened senescence of endometrial stromal cells?

3.3.1 Exploratory Outcome measures

1. Evaluate change of Lactobacillus-deplete microbiota to a Lactobacillus-dominated microbiota after treatment.

2. Assess changes in differentiation potential and colony-forming activity of endometrial stromal cells after treatment.

3. Assess senescence associated β Galactosidase activity in patients with CE.

The CERM trial Protocol

4. TRIAL DESIGN

This trial is a prospective, multi-centre, randomised, double blind adaptive designed trial, comparing a pre-conception course of doxycycline against placebo in up to 1500 women from sites in the United Kingdom. The trial is an adaptive design that allows frequent statistical review; leading to either continuation, stopping or adapting the trial to ensure maximal efficacy. Adaptive trial designs have the potential to markedly reduce the overall cost and duration of the trial by using interim statistical analysis, and modifying the design in the light of information already accumulated (e.g. stopping early or extending recruitment). Using ongoing pregnancy as a surrogate marker for live birth markedly reduces the overall cost and duration of the trial by reducing the time to knowledge of the outcome and builds in the necessary flexibility to enable an adaptive trial design. Our pragmatic primary outcome measure that is more meaningful to patients will be total live births, both actual, or anticipated, first live births, at the end of trial data collection including all completed, or ongoing, second or subsequent pregnancies after randomisation. The live birth outcome will include the effects doxycycline treatment may have on fertility, preterm birth, second trimester miscarriage and stillbirth.

We anticipate that around 3,062 women will have an endometrial biopsy, during the luteal phase of the women's menstrual cycle, to test for CE, defined as \geq 5 CD138 positive cells per 10mm². It is estimated that 50% will screen positive and be invited to participate in the randomised trial. Ongoing pregnancy at 12+6 weeks of gestation in the first pregnancy after randomisation is our primary explanatory outcome measure. Since 98% of all miscarriages occur prior to 12 weeks of pregnancy, ongoing pregnancy is a very good early marker of live births.³⁵

The trial comprises two stages:

- 1. Patients will be registered into the screening trial and have an endometrial biopsy taken to test for the presence of CE (N=3,062)
- 2. Women who screen positive for CE will be randomised into the randomised controlled trial of doxycycline versus placebo (N=1,500).

Within the main trial (CERM A) a subset of patients will be recruited to CERM B to determine if doxycycline treatment improves CE and microbiota compositions.

CERM B patients will all be recruited at University Hospital Coventry and Warwickshire NHS Trust. CERM B patients will follow the same pathway as CERM A patients but will have the following additional assessments:

- Patients will be registered into the screening trial, consented to the CERM B trial and have a vaginal, endometrial and cervical swab at registration.
- Women who screen positive for CE and are randomised into the trial will have a second endometrial biopsy following treatment.
- Women who screen positive for CE and are randomised into the trial will have a second vaginal, endometrial and cervical swab following treatment.

In order to analyse if doxycycline treatment improves CE and microbiota composition 200 paired endometrial biopsy and endometrial swab samples are required from patients before and after treatment. Approximately 400 patients will be registered into CERM B and have the additional vaginal, endometrial and cervical swab at registration. Approximately 200 of these patients will screen positive for CE and be randomised into the trial. These patients will have the repeated endometrial biopsy and vaginal, endometrial and cervical swab following treatment. A random sample of vaginal and cervical swabs will be analysed to ensure no contamination of the endometrial swab sample.

5. TRIAL SETTING

Women will be recruited from NHS Recurrent Miscarriage Clinics (RMC), Early Pregnancy Units (EPU) or through Tommy's 'Recurrent Miscarriage' database in 10 NHS organisations across the UK.

5.1 Site requirements:

- Sites must be able to take endometrial biopsy samples. Sites must adhere to the CERM A Manual for collection of Endometrial Biopsies for the collection, shipment and tracking of endometrial biopsy samples.
- Sites must follow pharmacy procedures detailed in the trial treatments section of the protocol, including IMP labelling, storage, dispensing and accountability procedures.
- Sites must adhere to the data collection requirements given in the data management section of the protocol.
- Sites must comply with the CERM Trial monitoring procedures set out in the monitoring, audit & inspection section of the protocol.

All NHS organisations taking part in the trial will be responsible for registering and randomising patients into the CERM Trial.

University Hospitals Coventry & Warwickshire NHS Trust will also be responsible for recruiting CERM B patients.

5.2 Site Initiation

Before the trial can be initiated at site, the prerequisites for conducting the trial must be clarified and the organisational preparations made with the trial site. The trial manager will arrange a site initiation visit which must be attended by key trial personnel at the site including the PI and pharmacy lead. This visit involves a detailed presentation of the trial documents and discussion of unanswered questions. The PI is responsible for ensuring that all of the information presented at site initiation is passed on continuously to all those who are involved in the conduct of the trial

Following site initiation, the research team will be in regular contact with sites by email, telephone and face-to-face, to support with the day-to-day management of the trial, and identify and discuss any problems with compliance to the protocol, recruitment pathway, barriers to recruitment, 'Site File' completeness.

5.3 Site staff Training

5.3.1 Principle Investigator (PI)

An appropriate, medically qualified, PI should be identified at each NHS organisation. The PI will have overall responsibility for the conduct of the trial at site. The PI will be responsible for:

• Ensuring that the trial is conducted as set out in the protocol and supporting document

- Delegating trial related responsibilities only to suitably trained and qualified personnel and ensuring that those with delegated responsibilities fully understand and agree to the duties being delegated to them
- Ensuring that CVs and evidence of appropriate training for all Site staff are available in the Trial Site File
- Ensuring that all delegated duties are captured in the trial Delegation Log
- Ensuring all Adverse Events are documented and reported appropriately to the WCTU CERM trial team.
- Accountability for trial treatments at their site.
- Ensuring the trial is conducted in accordance with ICH GCP principles
- Allowing access to source data for monitoring, audit and inspection
- Ensuring that all source data is complete and provided to the WCTU CERM trial team at regular intervals.

5.3.2 Research Team at site

All staff involved in trial specific duties will be required to have completed a Good Clinical Practice course and keep their knowledge up-to-date throughout the life-time of the trial.

5.3.3 Clinicians confirming eligibility

Clinicians confirming patient eligibility must be medically qualified.

5.3.4 Clinicians performing endometrial biopsies and vaginal, endometrial and cervical swabs

Clinicians taking biopsies and swabs will be competent to do so either by virtue of clinical role or appropriate specialist training on the technique for the trial (provided by CI or delegate). Trial specific guidance will be provided in the CERM A Manual for collection of Endometrial Biopsies and CERM B Manual for collection of Microbial Swabs. Clinicians taking biopsies and swabs are not required to have GCP training or be on the site delegation log if this procedure is routine in their clinical role.

6. ELIGIBILITY CRITERIA

As per GCP the decision as to whether a patient is eligible for entry into the trial is considered a medical decision and therefore this decision must be made by a medically qualified doctor.

Appropriately qualified staff assigned this responsibility must be named on the trial delegation log.

Confirmation of eligibility must be documented in the patients' medical notes.

WCTU CERM trial team will be available to answer any queries regarding eligibility criteria prior to registering a patient into the trial.

6.1 Inclusion criteria - screening

- Age ≥18 to <42
- Two or more consecutive first trimester miscarriages
- Women who agree to use barrier methods of contraception during the following cycles: biopsy preparation, screening-biopsy, waiting for the results and during the intervention.

6.2 Exclusion criteria – screening

- Treatable cause(s) of RM for example:
 - o antiphospholipid antibody syndrome
 - o thyroid disease
 - parental karyotypical abnormalities.
- Known sub-septate uterus.
- Poorly controlled diabetes (HbA1c >48mmol/mol)
- Allergy to doxycycline or its excipients.
- Doxycycline contraindicated
- Antibiotics in the current menstrual cycle
- Taking a medication that may interact with doxycycline refer to table 8 for a full list.
- Myasthenia Gravis.
- Systemic lupus erythematosus (SLE).
- Immunodeficiency disorder.
- Alcohol dependency*
- Long-term antibiotic(s) use.
- Menstrual cycle $\leq 21 \geq 42$ days.
- Unable to give informed consent.
- Participation in another clinical trial of an investigational medicinal product (CTIMP) in the last 90 days.
- Women who are breast feeding.
- Pregnancy

6.3 Inclusion criteria - RCT

• Women with \geq 5 CD138+ cells/10mm².

6.4 Exclusion criteria – RCT

- A course of antibiotics between screening registration and randomisation to RCT**
- A delay of longer than three months between biopsy result and randomisation to RCT**
- Known serious liver disease*1
- Taking a medication that may interact with doxycycline refer to table 8 for a list of known interactions.
- Any co-morbid disease or condition that would make the patient unsuitable for the trial^{*1}
- Pregnancy

* As judged by a medically qualified doctor assessing trial eligibility informed by referral letter from GP and hospital records

**If a woman has a course of antibiotics between screening registration and randomisation or was registered for screening over three months before randomisation to the RCT they will not be eligible for trial randomisation at the time. These women should be given the option to re-screen and have another biopsy to confirm eligibility for randomisation.

¹ If a clinician has doubts about a participants' suitability for the trial because of a long-term medical condition they should undertake a Full Blood Count (FBC) and Liver function tests (LFTs); in order for a woman to be included in the trial the following should apply:

- WBC >3x10⁹/L,
- Neutrophils >1.5x10⁹/L,
- Platelets >75x10⁹/L, Hb>100g/L
- Bilirubin <1.5XULN*
- AST/ALT <3xULN*
- Albumin >30g/dL).
- * ULN = Upper Limit of Normal

All required additional checks must be documented in the patients' medical notes

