7.3 Screening

To enter the trial women will be asked to consent to use contraception for either two or four menstrual cycles depending on whether they screen positive for CE (Table 7). However, this may be longer if a women does not use contraception, has a condom failure during one of the cycles or personal circumstances intervene.

Table	7 –	trial	cycles
-------	-----	-------	--------

Cycle	Procedure
1	Biopsy preparation
2	Screening: endometrial biopsy, microbial swab of the vagina*, endometrium*
	and cervix* and if there is an indication of liver failure a blood test may be taken
3	Results of screening
4	RCT for screen positive women
*CEBM E	2 only

*CERM B only

The endometrial biopsy will be taken in the luteal phase of the cycle at around (10 ± 4) days after ovulation. Instructions in the 'biopsy preparation kit' will request women to record their menstrual cycle, starting from the first day of bleeding in their next period, using the period tracker provided. The instructions will emphasise the importance of using condoms and not having unprotected sexual intercourse. Condoms are provided and more can be obtained by contacting the hospital research team, family planning services and some GP surgeries.

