8.6.5 Precautions in hepatic failure

Participants who develop signs of hepatic failure during treatment should have IMP discontinued and be treated with standard medical care.

A clinical assessment will be made at the start of the trial and if the investigator feels there is a clinical need to have additional blood test monitoring then this can be done at the discretion of the clinician.

Women will be excluded if they have any symptoms or history of liver failure – if clinically indicated then a blood test can be done.

If applicable, CTCAE grade 1 toxicity (Bilirubin <1.5xULN, AST/ALT <3xULN, Albumin >30g/dL) will be acceptable for entry and ongoing participation into the trial.

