8.7 Dosage modifications

Dose reductions and dose delays are not permitted in the trial. Treatment will be discontinued for the following reasons:

- Hypersensitivity reaction to doxycycline/placebo or excipients.
- Infection.
- Participant is required to take any other antibiotics concomitantly with doxycycline/placebo.
- Pregnancy or breast feeding.
- Visual disturbances (including loss of vision) or benign intracranial hypertension.
- Haematological toxicity greater than CTCAE grade 1.
- Hepatic toxicity greater than CTCAE grade 1.
- Rashes including maculopapular and erythematous rashes.
- Non-compliance with medication.

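### The albumin floor for trial entry is given in g/dL, ten times the evident intention, so no woman whose albumin is measured can meet it as written

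*Protocol*

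**What the plan says.** Section 6.4 of the protocol attaches footnote 1 to two exclusion criteria for the randomised trial: serious liver disease, and any comorbidity that makes the woman unsuitable. If a clinician has doubts "because of a long-term medical condition they should undertake a Full Blood Count (FBC) and Liver function tests (LFTs"). The footnote then sets a condition: "in order for a woman to be included in the trial the following should apply". The limits that follow cover white cells, neutrophils, platelets, haemoglobin, bilirubin and transaminases, and end with "Albumin >30g/dL".

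Section 8.6.5, on precautions in hepatic failure, gives the same hepatic limits in brackets after the words for CTCAE grade 1 toxicity: "AST/ALT <3xULN, Albumin >30g/dL) will be acceptable for entry and ongoing participation into the trial".

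Section 8.7 lists "Hepatic toxicity greater than CTCAE grade 1" among the reasons for stopping treatment.

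On when blood is taken, Table 7 in section 7.3 says that "if there is an indication of liver failure a blood test may be taken", and section 8.6.5 leaves testing to the clinician. Sections 9.1, 9.3 and 9.4 list no routine blood test.

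**The concern.** An albumin of 30 g/dL is not a physiological value. A lower limit that cannot be exceeded turns a check meant to tolerate mild abnormality into one that everybody fails.

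A site that orders the test then has two choices. It can exclude a woman whose liver function may be normal, or it can randomise her against a written criterion that she does not meet. The second is more likely, and it leaves source data at odds with the protocol. Section 6 requires eligibility to be documented in the medical notes, section 6.4 requires the additional checks to be documented there too, and section 15.3 has monitors compare trial records with source documents. If sites simply pass over the line, the intended albumin floor is not reliably applied to the women for whom the test was ordered. The wording in section 8.6.5 carries the same problem into continued participation.

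**Working it through.** The limit is a clinical cut-off, so there is no calculation in the plan to reproduce. The check is a unit conversion and a comparison of sections.

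**Inputs**
- Albumin floor: above 30 g/dL (protocol 6.4 footnote 1; repeated in 8.6.5).
- Unit of the other mass concentration in the 6.4 list: g/L, in "Platelets >75x10⁹/L, Hb>100g/L".
- Normal adult serum albumin: about 35 to 50 g/L. This is an assumption, because the protocol gives no reference range. A deliberately wide range of 20 to 60 g/L is used as a sensitivity check.

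**Conversion**
1 dL = 0.1 L, so x g/dL = 10x g/L.
30 g/dL × 10 = 300 g/L.

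**Comparison with attainable values**

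| Albumin (assumed) | Written floor ÷ value |
|---|---|
| 50 g/L | 300 / 50 = 6.0 |
| 35 g/L | 300 / 35 = 8.6 |
| 60 g/L (wide range) | 300 / 60 = 5 |
| 20 g/L (wide range) | 300 / 20 = 15 |

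The floor is 5 to 15 times too high even over the wide range, so the conclusion does not depend on the exact range assumed.

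**With the unit changed to g/L**
The floor becomes 30 g/L (3.0 g/dL), just below the assumed normal range. Every value from 35 to 50 g/L passes. That fits section 8.6.5, which presents the limits as acceptable grade 1 toxicity.

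**Slip in the protocol or fault in reading the PDF?**
- The same figure and unit appear in two separate sections, so a reading fault is unlikely.
- In 6.4 the albumin item ends with a closing bracket that has no opening partner. In 8.6.5 the same list is properly bracketed. This suggests that the text was copied from one section to the other with the unit already wrong.
- No other section gives albumin in g/L or corrects the unit.

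**The case against.** The strongest reply is that this is an editorial misprint with almost no consequence.

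- Testing happens only when a clinician has doubts, and no blood test is on the routine assessment lists. Few women are exposed.
- Only a medically qualified doctor may decide eligibility, and the trial team answers queries (section 6). With haemoglobin in g/L in the same list, and the limits described as tolerating grade 1 toxicity, a doctor comparing a laboratory report with the list would probably see the slip and not exclude every woman tested.
- The stopping rule in section 8.7 refers to the CTCAE grade and not to the albumin figure, so the error reaches treatment discontinuation only indirectly, through the wording of 8.6.5.
- No estimate, power figure or analysis changes.

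All of this stands, and it limits how much weight the point deserves. It does not make the criterion right. The figure is a binding decision limit, and as it stands the protocol relies on each site noticing the error for itself and departing from the text. How many would do so cannot be settled from the protocol.

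**Conclusion.** The albumin limit is wrong as written in both sections 6.4 and 8.6.5. It is a factor of 10 above the evident intention: 300 g/L written, against 30 g/L if g/L was meant. It lies 6.0 to 8.6 times above an assumed normal range of 35 to 50 g/L, and no plausible range makes it attainable. That g/L was intended is an inference from the haemoglobin unit and the grade 1 description; the clinical team should confirm it.

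The number of women affected is unknown and probably small, because only those given the discretionary test are exposed. The consequence is an unusable eligibility and safety limit and possible record mismatches, with no effect on design, sample size or analysis. It should be corrected, but it does not rank with points that bear on the trial's conclusions.

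**What to change.** Change g/dL to g/L, so that the limit reads albumin above 30 g/L, in footnote 1 to section 6.4 and in section 8.6.5. Have the clinical team confirm that 30 g/L is the intended floor, and carry the correction into any eligibility form or site guidance that repeats the figure. The stray closing bracket in 6.4 can be removed at the same time.

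The cost is one unit in two places, plus any dependent forms. Randomisation, sample size and analysis do not change.

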6.5 CERM B Exclusion (repeat endometrial biopsy and vaginal, cervical and endometrial swabs)

• Pregnancy

7. TRIAL PROCEDURE

[figure not shown]

Figure 2 – Pathways to recruitment

7.1 Patient Identification

Women will be identified to participate in one of the following two ways:

7.1.1 Women on the Tommy's 'Recurrent Miscarriage' database

Women on the Tommy's 'Recurrent Miscarriage' database have had investigations for a treatable cause of their miscarriage and have given consent to be contacted for research purposes. These women will be sent an introduction letter and a screening participant information sheet explaining about the trial and what participation would involve, either by post or email depending on their stated preference. After one week women will be contacted, by telephone, by a member of the hospital research team to discuss the trial, answer any questions and discuss participation.

7.1.2 Women referred to a recurrent miscarriage clinic

Women with a clinician referral to a recurrent miscarriage clinic from a gynaecologist, obstetrician, EPU or General Practitioner (GP) who have not had investigations into the cause of their RM will be sent an appointment to attend for investigations as per standard practice by the direct care team.

Separately a member of the hospital research team will send women an introduction letter and a screening participant information sheet explaining about the trial and what participation would involve and inviting women to contact a member of the hospital research team if they would like more information or to participate in the trial.

If a treatable cause of their recurrent miscarriages is identified they will receive treatment and will not be eligible for the trial. If a treatable cause of their recurrent miscarriages is not identified they will be eligible for the trial.

If women on either pathway would prefer to talk about the trial and what participation would mean for them face-to-face this will be arranged.

Women who self-refer will be advised to contact their GP to discuss referral to one of the recurrent miscarriage clinics taking part in the trial.

7.1.3 Screening Log

A Screening Log must be maintained by each site to document all patients considered for the trial even if subsequently not entered into the trial. Where possible, the reason for non-entry to the trial must be documented. This must be faxed or emailed to WCTU CERM trial team on a regular basis when requested. Patient names or hospital numbers must not be recorded on the Screening Log.

7.2 Pre-Screening

It is important to women, who are trying to conceive, to minimise the time they are using contraception, therefore to reduce this time we are asking women to prepare for their biopsy before they attend clinic. If women on either pathway would like to participate, their initial eligibility will be checked and verbal consent will be taken and documented in their medical notes. Confirmation of verbal consent should also be recorded on the CERM trial screening

log. A biopsy preparation kit which includes a period tracker, condoms and a ovulation testing kit will be posted out or given to women if they meet face-to-face with a member of the hospital research team. Instructions on using the kit will be included. Women will contact the clinic when they are ovulating or if the test does not indicate ovulation on day 23, to arrange to come into clinic for a biopsy.

